### **3. INTRODUCTION**

This SAP has been developed after review of the Clinical Study Protocol (final version dated 11 September 2020) and Protocol Amendment (a) (final version dated 16 September 2020).

This SAP describes the planned analysis of the safety, tolerability and pharmacokinetic (PK) data from this study. A detailed description of the planned TFLs to be presented in the clinical study report (CSR) is provided in the accompanying TFL shell document.

The intent of this document is to provide guidance for the statistical and PK analyses of data. In general, the analyses are based on information from the protocol, unless they have been modified by agreement with Eli Lilly and Company. A limited amount of information concerning this study (e.g., objectives, study design) is given to help the reader's interpretation. This SAP must be signed off prior to first participant visit for this study. When the SAP and TFL shells are agreed upon and finalized, they will serve as supporting material for this study's CSR.

This SAP supersedes the statistical considerations identified in the protocol; where considerations are substantially different, they will be so identified. If additional analyses are required to supplement the planned analyses described in this SAP, they may be performed and will be identified in the CSR. Any substantial deviations from this SAP will be agreed upon with Eli Lilly and Company and identified in the CSR. Any minor deviations from the TFLs may not be documented in the CSR.

This SAP is written with consideration of the recommendations outlined in the International Conference on Harmonisation (ICH) E9 Guideline entitled Guidance for Industry: Statistical Principles for Clinical Trials and the ICH E3 Guideline entitled Guidance for Industry: Structure and Content of Clinical Study Reports.

### **4. STUDY OBJECTIVES**

#### **4.1 Primary Objective**

The primary objective of the study is to evaluate the effect of lasmiditan on P-glycoprotein (P-gp) and breast cancer resistance protein (BCRP) activity in healthy participants.

The primary endpoints of the study are maximum observed drug concentration ( $C_{max}$ ) and area under the concentration (AUC) versus time curve from time zero to infinity (AUC [0- $\infty$ ]) of dabigatran to assess P-gp activity and rosuvastatin to assess BCRP activity.

#### **4.2 Secondary Objectives**

The secondary objectives of the study are:

- To evaluate the safety and tolerability of dabigatran etexilate or rosuvastatin in combination with lasmiditan in healthy participants
- To evaluate the pharmacokinetics of lasmiditan and M8

[figure not shown]
The secondary endpoints of the study are:

- A summary of the number of treatment-emergent adverse events (TEAEs) and serious adverse events (SAE)
- $C_{max}$  of lasmiditan and M8
- Time of maximum observed drug concentration ( $t_{max}$ ) of lasmiditan and M8
- AUC (0- $\infty$ ) of lasmiditan and M8

## 5. STUDY DESIGN

This is a Phase 1, two-part, two-period, open-label study in healthy participants. Part 1 will study dabigatran P-gp drug-drug interaction (DDI) with lasmiditan. Part 2 will study rosuvastatin BCRP DDI with lasmiditan. Parts 1 and 2 will have a similar design, i.e., dabigatran etexilate or rosuvastatin administration alone in Period 1 (Day 1) followed by a brief washout, then lasmiditan on Days 8, 9, and 10 (Period 2) with coadministration of dabigatran etexilate or rosuvastatin with lasmiditan on Day 10. Each part will consist of different participants and the 2 parts may run in parallel. Participants for both Part 1 and Part 2 will be consented with a single consent form, and both genotyping and coagulation tests will be performed for both parts during screening. Part 2 will be prioritized to complete first due to an anticipated screen fail rate of ~50% secondary to genotype criteria. Once Part 2 has achieved last participant dosed, no further genotyping will be needed for LAIO screening. Participants who failed Part 2 screening due to genotyping only and have a normal coagulation profile will automatically be eligible for Part 1.

A general schema for this study can be seen in [Figure 1](#).

**Figure 1 – General schema for LAIO**

## 6. TREATMENTS

The following is a list of the study treatment abbreviations that will be used in the TFLs.

Part	Day	Study Treatment Name	Treatment order in TFL
1	1	150 mg dabigatran etexilate	1
	8-9	200 mg lasmiditan	2
	10	150 mg dabigatran etexilate + 200 mg lasmiditan	3
2	1	10 mg rosuvastatin	4
	8-9	200 mg lasmiditan	5
	10	10 mg rosuvastatin + 200 mg lasmiditan	6

## 7. SAMPLE SIZE JUSTIFICATION

Approximately 72 participants will be enrolled to Part 1 of the study to ensure that at least 62 evaluable participants complete that part. With 62 participants, we expect the two 1-sided t-tests (TOSTs) for equivalence applied to the log-normal mean ratio to have a power of at least 80% for the AUC (0- $\infty$ ) and Cmax tests in Part 1. This assumes a nominal expected mean ratio of 1.05, a coefficient of variation (CV) of 39.3%, and a significance level of 0.05 of each 1-sided test when testing against an upper limit of 1.25 and a lower limit of 0.80. The tests will be displayed in the form of 90% confidence intervals (CI), which are equivalent to the according TOST. The source of the CV is Boehringer Ingelheim bioequivalence study (EudraCT number 2007-005765-35), and the higher intrasubject CV observed in the second-generation dabigatran arm was chosen.

Approximately 32 participants will be enrolled to Part 2 to ensure that at least 28 evaluable participants complete that part. With 28 participants, we expect the TOSTs for equivalence applied to the lognormal mean ratio to have a power of at least 80% for the AUC(0- $\infty$ ) and Cmax tests in Part 2. This assumes a nominal expected mean ratio of 1.05, a CV of 25.1%, and significance level of 0.05 of each 1-sided test when testing against an upper limit of 1.25 and a lower limit of 0.80. The tests will be displayed in the form of 90% CI which are equivalent to the according TOST. The source of the CV is Study AZEB, and the higher of the rosuvastatin AUC(0- $\infty$ ) and Cmax intrasubject CVs was chosen.

## 8. DEFINITION OF ANALYSIS POPULATIONS

The “Entered” population will consist of all participants who signed the informed consent form (ICF).

The “Enrolled” population will consist of all participants assigned to treatment, regardless of whether they take any doses of study intervention, or if they took the correct treatment.

The “Safety” population will consist of all participants assigned to dabigatran etexilate or rosuvastatin and who take at least 1 dose of 1 of those products. Participants will be analyzed according to the product they actually received.

---

The “Pharmacokinetic” population will consist of all participants who receive at least 1 dose of dabigatran etexilate or rosuvastatin and have evaluable PK.

All protocol deviations that occur during the study will be considered for their severity/impact and will be taken into consideration when participants are assigned to analysis populations.

## **9. STATISTICAL METHODOLOGY**

### **9.1 General**

Data listings will be provided for all data that is databased. Summary statistics and statistical analysis will only be presented for data where detailed in this SAP. For continuous data, summary statistics will include the arithmetic mean, arithmetic standard deviation (SD), median, min, max and N; for log-normal data (e.g. the PK parameters: AUCs and  $C_{max}$ ) the geometric mean and geometric CV will also be presented. For categorical data, frequency count and percentages will be presented. Data listings will be provided for all participants up to the point of withdrawal, with any participants excluded from the relevant population highlighted. Summary statistics and statistical analyses will generally only be performed for participants included in the relevant analysis population. For the calculation of summary statistics and statistical analysis, unrounded data will be used.

Mean change from baseline is the mean of all individual participants' change from baseline values. Each individual change from baseline will be calculated by subtracting the individual participant's baseline value from the value at the timepoint. The individual participant's change from baseline values will be used to calculate the mean change from baseline using a SAS procedure such as PROC UNIVARIATE.

Data analysis will be performed using SAS® Version 9.4 or greater.

### **9.2 Demographics and Participant Disposition**

Participant disposition will be summarized and listed. The demographic variables age, sex, race, ethnicity, body weight, height and body mass index will be summarized and listed. All other demographic variables will be listed only.

### **9.3 Pharmacokinetic Assessment**

#### **9.3.1 Pharmacokinetic Analysis**

Noncompartmental methods applied with a validated software program (WinNonlin Phoenix v8.1 or later) to the plasma concentrations of dabigatran, rosuvastatin, lasmiditan and its metabolite M8 will be used to determine the following PK parameters, when possible:

Parameter	Units	Definition
AUC(0-t last )	ng*h/mL	area under the concentration versus time curve from time zero to time t, where t is the last time point with a measurable concentration
AUC(0-∞)	ng*h/mL	area under the concentration versus time curve from time zero to infinity
%AUC(t last -∞)	%	percentage of AUC(0-∞) extrapolated
C max	ng/mL	maximum observed drug concentration
t max	h	time of maximum observed drug concentration
t 1/2	h	half-life associated with the terminal rate constant ( $\lambda_z$ ) in non-compartmental analysis
CL/F	L/h	apparent total body clearance of drug calculated after extra-vascular administration (not M8)
V Z /F	L	apparent volume of distribution during the terminal phase after extra-vascular administration (not M8)
V ss /F	L	apparent volume of distribution at steady state after extra-vascular administration (not M8)

Additional PK parameters may be calculated, as appropriate. The software and version used for the final analyses will be specified in the clinical study report. Any exceptions or special handling of data will be clearly documented within the final study report.

Formatting of tables, figures and abbreviations will follow the Eli Lilly Global PK/PD/TS Tool: NON-COMPARTMENTAL PHARMACOKINETIC STYLE GUIDE. The version of the tool effective at the time of PK analysis will be followed.

### General PK Parameter Rules

- Actual sampling times will be used in the final analyses of individual PK parameters, except for non-bolus pre-dose sampling times which will be set to zero.
- Cmax and tmax will be reported from observed values. If Cmax occurs at more than one time point, tmax will be assigned to the first occurrence of Cmax.
- AUC parameters will be calculated using a combination of the linear and logarithmic trapezoidal methods (linear-log trapezoidal rule). The linear trapezoidal method will be applied up to tmax and then the logarithmic trapezoidal method will be used after tmax. The minimum requirement for the calculation of AUC will be the inclusion of at least three consecutive plasma concentrations above the lower limit of quantification (LLOQ), with at least one of these concentrations following Cmax. AUC(0-∞) values where the percentage of the total area extrapolated is more than 20% will be flagged. Any AUC(0-∞) value excluded from summary statistics will be noted in the footnote of the summary table.
- Half-life (t1/2) will be calculated, when appropriate, based on the apparent terminal log-linear portion of the concentration-time curve. The start of the terminal elimination phase for each participant will be defined by visual inspection and generally will be the first point at which there is no systematic deviation from the log-linear decline in plasma

concentrations. Half-life will only be calculated when a reliable estimate for this parameter can be obtained comprising of at least 3 data points. If  $t_{1/2}$  is estimated over a time window of less than 2 half-lives, the values will be flagged in the data listings. Any  $t_{1/2}$  value excluded from summary statistics will be documented in the footnote of the summary table.

- A uniform weighting scheme will be used in the regression analysis of the terminal log-linear portion of the concentration-time curve.
- The parameters based on predicted  $C_{last}$  will be reported.

### **Individual PK Parameter Rules**

- Only quantifiable concentrations will be used to calculate PK Parameters with the exception of special handling of certain concentrations reported below the lower limit of quantification (BQL). Plasma concentrations reported as BQL will be set to a value of zero when all of the following conditions are met:
- The compound is non-endogenous.
- The samples are from the initial dose period for a participant or from a subsequent dose period following a suitable wash-out period.
- The time points occur before the first quantifiable concentration.
- All other BQL concentrations that do not meet the above criteria will be set to missing.
- Also, where two or more consecutive concentrations are BQL towards the end of a profile, the profile will be deemed to have terminated and therefore any further quantifiable concentrations will be set to missing for the calculation of the PK parameters unless it is considered to be a true characteristic of the profile of the drug.

### **Individual Concentration vs. Time Profiles**

- Individual concentrations will be plotted utilizing actual sampling times.
- The terminal point selections will be indicated on a semi-logarithmic plot.

### **Average Concentration vs. Time Profiles**

- The average concentration profiles will be graphed using scheduled (nominal) sampling times.
- The average concentration profiles will be graphed using arithmetic average concentrations.
- The pre-dose average concentration for single-dose data from non-endogenous compounds will be set to zero. Otherwise, only quantifiable concentrations will be used to calculate average concentrations.
- Concentrations at a sampling time exceeding the sampling time window specified in the protocol, or  $\pm 10\%$ , will be excluded from the average concentration profiles.
- Concentrations excluded from the mean calculation will be documented in the final study report.
- A concentration average will be plotted for a given sampling time only if 2/3 of the individual data at the time point have quantifiable measurements that are within the sampling time window specified in the protocol or  $\pm 10\%$ . An average concentration

estimated with less than 2/3 but more than 3 data points may be displayed on the mean concentration plot if determined to be appropriate and will be documented within the final study report.

### **Treatment of Outliers during Pharmacokinetic Analysis**

Application of this procedure to all pharmacokinetic analyses is not a requirement. Rather, this procedure provides justification for exclusion of data when scientifically appropriate. This procedure describes the methodology for identifying an individual value as an outlier for potential exclusion, but does not require that the value be excluded from analysis. The following methodology will not be used to exclude complete profiles from analysis.

#### Data within an Individual Profile

A value within an individual profile may be excluded from analysis if any of the following criteria are met:

- For pharmacokinetic profiles during multiple dosing, the concentration of the pre-dose sample exceeds all measured concentrations for that individual in the subsequent post-dose samples.
- For pharmacokinetic profiles during single dosing of non-endogenous compounds, the concentration in a pre-dose sample is quantifiable.
- For any questionable datum that does not satisfy the above criteria, the profile will be evaluated and results reported with and without the suspected datum.

#### Data between Individual Profiles

1. If  $n < 6$ , then the dataset is too small to conduct a reliable range test. Data will be analyzed with and without the atypical value, and both sets of results will be reported.
2. If  $n \geq 6$ , then an objective outlier test will be used to compare the atypical value to other values included in that calculation:
  - a. Transform all values in the calculation to the logarithmic domain.
  - b. Find the most extreme value from the arithmetic mean of the log transformed values and exclude that value from the dataset.
  - c. Calculate the lower and upper bounds of the range defined by the arithmetic mean  $\pm 3*SD$  of the remaining log-transformed values.
  - d. If the extreme value is within the range of arithmetic mean  $\pm 3*SD$ , then it is not an outlier and will be retained in the dataset.
  - e. If the extreme value is outside the range of arithmetic mean  $\pm 3*SD$ , then it is an outlier and will be excluded from analysis.

If the remaining dataset contains another atypical datum suspected to be an outlier and  $n \geq 6$  following the exclusion, then repeat step 2 above. This evaluation may be repeated as many times

as necessary, excluding only one suspected outlier in each iteration, until all data remaining in the dataset fall within the range of arithmetic mean  $\pm 3 \times \text{SD}$  of the log-transformed values.

Reporting of Excluded Values

Individual values excluded as outliers will be documented in the final report. Approval of the final report will connote approval of the exclusion.

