2.2. Background

In previous studies, following single oral dose administration of lasmiditan to adult participants, lasmiditan was absorbed with a median time of maximum observed drug concentration (t_{max}) of 1.8 hours, and rapidly eliminated with a mean half-life associated with the terminal elimination phase (t_{1/2}) of approximately 5.7 hours. Lasmiditan undergoes extensive hepatic and extrahepatic metabolism with ketone reduction to inactive metabolite M8 as the major biotransformation pathway. No accumulation of lasmiditan was observed with daily dosing. More detailed information about the PK and absorption, distribution, metabolism, and excretion properties of lasmiditan may be found in the IB.

Dabigatran etexilate, a competitive, direct thrombin inhibitor, is a P-gp substrate. Following absorption, dabigatran etexilate is hydrolyzed to form dabigatran, the active moiety. Dabigatran concentrations reach t_{max} within 2 hours of administration, and then concentrations decline in a biphasic manner, with a terminal t_{1/2} of 12 to 17 hours. Dabigatran is primarily eliminated through renal excretion and does not appear to be a substrate for renal transporters based on the reported renal clearance of 89 mL/min (Stangier 2008). Dabigatran itself is not a substrate for the cytochrome P450 (CYP) family of metabolizing enzyme nor a substrate for P-gp, meaning that

changes in dabigatran exposure following administration of a P-gp inhibitor would be anticipated to only reflect the activity of the inhibition of dabigatran etexilate transport at the intestinal wall (Stangier 2008). Previous studies have investigated the effect of P-gp inhibitors on dabigatran PK. Dabigatran area under the concentration versus time curve (AUC) increased by 58% and 53% when co-administered with amiodarone and quinidine, respectively (Pradaxa® Prescribing Information, 2010). Ketoconazole, a strong P-gp inhibitor, increased dabigatran AUC and C_{max} values by 138% and 135%, respectively, after a single dose of 400 mg, and 153% and 149%, respectively, after multiple daily 400-mg doses (Pradaxa Prescribing Information, 2010).

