9.1. Statistical Hypotheses

There is no direct control for multiplicity but both primary objective variables will be tested as co- confirmatory variables. All other tests and/or estimation statistics will not be confirmatory but will contribute to a body of evidence to support final conclusions.

No significant DDI for dabigatran or rosuvastatin will be concluded if the respective 90% confidence interval for AUC from time zero to infinity (AUC[0- ∞]) and C_{max} is completely contained within the no-effect boundaries (0.80, 1.25). A description of each test is provided in Section 9.4.

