9.4. Statistical Analyses

Statistical analysis of this study will be the responsibility of the sponsor or its designee.

Pharmacokinetic analyses will be conducted on data from all participants who receive at least 1 dose of lasmiditan and have evaluable PK. Statistical inference of PK parameters will utilize participants in the PK analysis population which have evaluable PK, both before and after the introduction of lasmiditan.

Safety analyses will be conducted for all enrolled participants who received at least 1 dose of dabigatran etexilate or rosuvastatin, whether or not they completed all protocol requirements.

Additional exploratory analyses of the data will be conducted as deemed appropriate.

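### With six or more values, as in both parts, the SAP lets a 3-SD rule drop data without a documented cause, promises no all-data result, and leaves open whether exclusion is optional and what is tested

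*SAP*

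**What the plan says.** The outlier procedure is in SAP 9.3.1.

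- **Six or more values, between profiles.** Values are log-transformed and the most extreme is set aside. It is then compared with the mean ± 3 SD of the remainder. If it lies outside, "then it is an outlier and will be excluded from analysis". The step may be repeated without a cap while at least six values remain.
- **Fewer than six values.** No test is applied: "Data will be analyzed with and without the atypical value, and both sets of results will be reported".
- **Within one profile.** For a questionable value that meets none of the listed criteria, "the profile will be evaluated and results reported with and without the suspected datum".
- **Status of the procedure.** The introduction says it identifies values for potential exclusion, "but does not require that the value be excluded from analysis". It offers itself as justification where exclusion is scientifically appropriate, without saying what that means. It also says complete profiles will not be excluded this way.
- **What is tested.** The rule is used to "compare the atypical value to other values included in that calculation". The calculation is not identified.
- **Reporting.** Excluded values are documented in the final report, and approval of the report counts as approval of the exclusion.

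SAP 9.3.2 specifies the mixed models for log Cmax and log AUC(0-∞) and does not say whether the outlier rule applies to them. Protocol 9.4 bases inference on participants "which have evaluable PK, both before and after the introduction of lasmiditan". Protocol 9.1 concludes no significant interaction if the 90% CIs for both parameters lie within 0.80 to 1.25.

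**The concern.** The with-and-without safeguard is written for the cases that will not carry the confirmatory analysis and is missing from the one that will. The sponsor could exclude a value on the 3-SD statistic alone, or keep it, and either choice is consistent with some sentence of the SAP. The sponsor could also choose, after seeing open-label data, whether to test each treatment's values or the within-participant ratios. Because inference needs evaluable data from both periods, removing one Cmax or AUC(0-∞) value can remove that participant's whole comparison for that parameter.

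The direction that matters is a false conclusion of no interaction. If lasmiditan affects most people little but a few people strongly, the strong responders are the values a 3-SD rule removes. Removing them both lowers the estimated ratio and narrows the interval.

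**Working it through.** **Inputs from the documents.** Evaluable n of 62 (Part 1) and 28 (Part 2); intrasubject CV 39.3% and 25.1%; expected ratio 1.05; 0.05 per one-sided test; limits 0.80 and 1.25 (Protocol 9.2, SAP 7). Published inhibitor effects on AUC (Protocol 2.2): single-dose ketoconazole on dabigatran +138%, a ratio of about 2.4; on rosuvastatin, eltrombopag +60% (1.6) and cyclosporine +610% (7.1).

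**Assumptions not in the documents.** Between-participant CV 50% (varied from 30% to 70%); two strong responders per part; an own ratio of 4 as an intermediate case. Every flagged value is taken to be excluded.

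**The plan's own figure.** With σ = √ln(1+CV²) and SE = σ√(2/n):

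- Part 1: σ = √ln(1+0.393²) = 0.379; SE = 0.379 × √(2/62) = 0.068; exact paired TOST power at 1.05 is 80.2%.
- Part 2: σ = √ln(1+0.251²) = 0.247; SE = 0.247 × √(2/28) = 0.066; power is 81.4%.

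The stated 80% reproduces in both parts, with little to spare. Losing one participant's pair gives 79.6% (Part 1) or 79.9% (Part 2).

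**How often the rule fires on valid data.** In 40,000 simulated sets of clean lognormal values, at least one value is flagged in 24.4% of sets at n=62 and 18.5% at n=28.

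**Effect on the decision.** Log value = participant effect + treatment effect + residual. The 90% CI is checked against 0.80 to 1.25 using all pairs, then the pairs left after applying the rule to each treatment's values, then the pairs left after applying it to log ratios (20,000 runs per scenario; simulation SE about 0.15 points near 5%, at most 0.35). In the subset scenarios two participants have the stated own ratio R, and the others are set so that the overall geometric mean ratio stays at 1.25:

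ratio for the others = exp{[n ln 1.25 − 2 ln R]/(n − 2)}

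For Part 2 and R = 4 this is exp{(28 × 0.2231 − 2 × 1.3863)/26} = 1.14; for R = 7.1 it is 1.09.

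Rate of concluding no interaction at an overall ratio of 1.25, one parameter:

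| Scenario | All data | Rule by treatment | Rule on ratios |
|---|---|---|---|
| Part 1, clean | 5.0% | 5.3% | 5.7% |
| Part 1, two at 2.4 | 4.8% | 5.3% | 6.1% |
| Part 1, two at 4 | 3.7% | 5.6% | 8.0% |
| Part 2, clean | 4.9% | 5.2% | 6.2% |
| Part 2, two at 1.6 | 4.7% | 5.0% | 6.0% |
| Part 2, two at 4 | 1.4% | 8.0% | 27.4% |
| Part 2, two at 7.1 | 0.2% | 31.1% | 59.7% |

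- **Clean data.** The rule leaves the mean ratio unchanged, and power at 1.05 moves by less than 1 point.
- **Opposite direction.** With two participants at a ratio of 0.25, the by-treatment rule lowers the rate from 3.2% to 2.2% (n=62) and from 0.3% to 0.2% (n=28).
- **Between-participant CV.** Moving it from 30% to 70% takes the Part 2 by-treatment result from 19.1% to 4.3% (ratio 4) and from 55.8% to 14.6% (ratio 7.1).
- **Heavy tails** (t with 3 df, assumed; rule on ratios; 12,000 runs). The false conclusion rate goes from 4.9% to 6.9% (Part 1) and from 4.8% to 7.2% (Part 2). Power at 1.05 goes from 82.0% to 95.1% and from 84.3% to 95.5%.

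Protocol 9.1 requires both parameters to pass, so joint rates are no higher than these.

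**The case against.** The best defence has five parts.

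1. **The rule is pre-specified.** The SAP is to be signed off before the first participant visit, and the scale, the 3-SD limit and the minimum n are fixed. That is true of the arithmetic of the test. Whether to invoke it, and on what, is not fixed.
2. **Complete profiles are protected.** This limit is real and sits awkwardly with the ratio reading, which removes both of a participant's values. It does not clearly protect a single Cmax or AUC(0-∞) value while the profile stays in the listings.
3. **The by-treatment reading fits the primary model better.** That model analyses values by treatment; ratios appear only in the exploratory genotype display. I agree that the by-treatment column deserves more weight. There, every scenario built on the protocol's own inhibitor figures except cyclosporine moves the error rate by at most half a point.
4. **The large figures are constructed.** Ratio 4 has no source in the documents, and 7.1 is a mean effect of cyclosporine rather than an individual response to lasmiditan. Part 2 also excludes impaired-function ABCG2 and SLCO1B1 genotypes, which removes one source of such spread. All of this stands. The figures show what the rule could do, not what is likely.
5. **An all-data interval could be recovered.** Data are listed and exclusions are documented or footnoted, so it could be. It is still not promised, and a listing is not a reported 90% CI.

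A narrower repair would add with-and-without reporting, name the quantity and align the wording, while keeping the rule in the primary analysis. That would remove most of the problem. It would still leave unclear which of two conflicting results carries the conclusion.

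**Conclusion.** The concern holds. For n of at least six, the SAP allows exclusion on a statistic alone, commits to no all-data result, contradicts itself on whether exclusion is optional, and does not name the tested quantity or the status of the primary models.

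The wording gap is certain; its effect on the conclusion depends on the data. With clean data or modest interactions the false no-interaction rate rises by between 0.3 and 1.3 points, and the rule can also work against a no-interaction claim. It becomes serious only for rare, strong responders, mainly in Part 2. There the choice of tested quantity alone separates 8.0% from 27.4% in the ratio-4 case. Those larger figures rest on an assumed number of responders, an assumed between-participant CV, and exclusion of every flagged value. The sample size is not in question. This should be fixed, but it does not undermine the design.

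**What to change.** In SAP 9.3.1 and 9.3.2:

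- State that the primary Cmax and AUC(0-∞) models use all evaluable values, and that a value is excluded only for a documented dosing, sampling or assay cause.
- Keep the 3-SD rule as a sensitivity analysis on a named quantity, for example log values within each treatment.
- Report results with and without excluded values at every n, as the SAP already does for fewer than six values and for questionable values within a profile.
- Reconcile the introduction to the outlier procedure, which makes exclusion optional, with step 2e, which makes it mandatory.

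The cost is SAP wording and one extra model run per parameter. No planned sample size or power figure changes. The drawback is a somewhat wider interval if an artefact with no documented cause is kept. If residuals are heavy-tailed, the power gain seen above from trimming is given up in the primary analysis, although the all-data analysis still had more than 80% power in those runs.
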